6.1.3.2 EORW (End of RW Period/LTE Baseline): Clinic Visit

The EORW visit will be same day as LTE-TP baseline visit.

All randomized subjects, including those that have had pericarditis recurrence or have permanently discontinued study drug will have an EORW visit at the end of the RW period. The EORW activities are listed below:

- Evaluate concomitant medications as well as pericarditis concomitant medications.

- Acquire a 12-lead ECG.
- Acquire and submit a cardiac ECHO to the core laboratory per the core laboratory imaging guidelines; the ECHO is to be read locally prior to submission to the core lab.
- Perform a full physical examination, height and body weight.
- For subjects ≥ 18 years, complete the SF-36, EQ-5D-5L, ISI.
- For all subjects, complete the PGIPS score.
- The investigator is to complete the PGA-PA.
- Obtain central laboratory samples for chemistry, hematology, lipid panel, CRP, PK, ADAs, and urinalysis.
- Assess for AEs.
- Assess for pericarditis recurrences.
- Obtain informed consent for participation in the LTE period.
- Additional discussion/assessment as needed.

Upon completion of the EORW visit procedures and obtaining subject informed consent to participate in the LTE period, the LTE baseline visit procedures are as follows:

- Change the subject's status in the IWRS and obtain unblinding information; proceed with subject unblinding.
- Obtain weight for pediatric drug dispensing and dosing (Table 5–1).
- Dispense study drug and record the amount (number of vials) dispensed.
- Have the subject administer the LTE-TP Day 1 study drug dose as applicable (if within the study drug window) and have the subject record it in the medication diary.
- Instruct subjects on continuing the 11-point pericarditis pain NRS score daily entry.
- Review the study drug dosing schedule, administration techniques, and documentation.
- Additional discussion/assessments as needed (i.e., remind the subject about daily pericarditis pain NRS input).
- Confirm the upcoming study visits.

6.1.4 Long Term Extension

6.1.4.1 LTE Weeks 8 and 16: Clinic Visit

The LTE Weeks 8 and 16 clinic visit procedures are as follows:

- Evaluate concomitant medications as well as pericarditis concomitant medications.
- Have all subjects complete the PGIPS score.
- The investigator is to complete the PGA-PA.
- Obtain central laboratory samples for chemistry, hematology, and CRP.
- Assess for AEs.
- Assess for pericarditis recurrence events.
- Additional discussion/assessment as needed (i.e., remind the subject about daily pericarditis pain NRS input).
- Confirm upcoming visit arrangements.
- Obtain weight for pediatric drug dispensing and dosing ([Table 5–1](#)).
- Dispense study drug through the IWRS and record the amount (number of vials) dispensed.
- Review the study drug dosing schedule, administration techniques, and documentation.
- Have the subject administer the regularly scheduled study drug dose as applicable (if within the study drug window) and have the subject record it in the medication diary.
- Confirm the upcoming study visits.

6.1.4.2 LTE Week 24 Clinic Visit

The LTE Week 24 visit is the final visit of the LTE-TP. However, if at any time throughout the course of the study a subject prematurely discontinues study drug, an End of Treatment (EOT) visit is to occur. The visit procedures are as follows:

- Evaluate concomitant medications as well as pericarditis concomitant medications.
- Acquire a 12-lead ECG.
- Acquire a cardiac ECHO for core laboratory central review; the ECHO is to be read locally prior to submission to the core lab.
- Obtain cardiac MRI (substudy participants only).
- Perform a full physical examination.
- For subjects ≥ 18 years, complete the SF-36, EQ-5D-5L, ISI.
- For all subjects, complete the PGIPS score.
- The investigator is to complete the PGA-PA.

- Obtain central laboratory samples for chemistry, hematology, lipid panel, CRP, PK, ADAs, biomarkers, and urinalysis.
- Assess for AEs.
- Assess for pericarditis recurrence events.
- Have the subject administer the regularly scheduled study drug as applicable (if within study drug window), and have the subject record it in the medication diary.
- Change the subject status in the IWRS.
- Arrange an LTE Week 30 visit.

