^h Lipid panels are non-fasting and are to be drawn at a minimum of every 6months during the randomization withdrawal and LTE periods, or more frequently as needed, with mandated evaluations as detailed in the schedule of events.

^j For women of child bearing potential - urine pregnancy testing can be repeated as needed throughout the course of the study and serum pregnancy can be drawn as needed; urine pregnancy is required to be performed at enrollment and 6 weeks after the last dose of study drug.

^l Adverse event reporting begins following the subject providing informed consent.

^m All procedures are to be completed prior to study drug administration.

^o Study drug administration is once weekly with a minimum of 5 days required between doses.

^t The EORW visit serves as both the last visit of the RW period and the baseline visit of the LTE period.

^u For all subjects, the final clinic visit of the end of RW period is to be scheduled once the End of the Randomization Withdrawal end date is announced by Sponsor. This includes subjects that are taking blinded study drug, open-label rilonacept, or who have prematurely discontinued study drug.

^v Study drug administration to occur only after subject provides informed consent for the open-label extension period.

Table 1–3 Study Schedule of Activities – Long Term Extension (Part 1 of 2)

Trial Period	LONG TERM EXTENSION (48 WEEKS)				
	Long Term Extension Treatment (24 Weeks) ^m			Long Term Extension Follow Up (24 Weeks)	
Visit Name	LTE Week 8	LTE Week 16	LTE Week 24	LTE Week 30	EOS/ LTE Week 48
Visit Window ^b (days)	+/- 2	+/- 2	+/- 2	+/- 2	+/- 2
Visit Type	Clinic	Clinic	Clinic	Clinic	TC
Concomitant medications	X	X	X	X	X
Pericarditis Concomitant medications	X	X	X	X	X
Full Physical Examination ^c			X		
12-Lead ECG			X		
Echo ^e			X		
MRI (substudy only)			X		
Pericardial pain (11-point NRS)	DAILY				
EQ-5D			X		
SF-36			X		
ISI			X		
PGIPS	X	X	X		
PGA-PA	X	X	X		

^b Scheduling of visits within visit windows requires cautious planning to ensure there is no interruption to subject evaluation and study drug treatment.

^c Full physical examination includes at minimum evaluation of vital signs, head, eye, ear, nose, and throat as well as cardiovascular, dermatological, musculoskeletal, respiratory, GI, genitourinary, and neurological systems

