6.1.3 Randomized-Withdrawal (RW) Period

During the RW period, subjects will continue with once-weekly study drug administration as well as daily 11-point pericarditis pain NRS scoring. Visits will occur every 4 weeks, alternating TC/RN visits and clinic visits, with the first visit during the RW period (RW Week 4) being a TC/RN visit. Additional unscheduled visits may occur at any time for evaluation of suspected pericarditis recurrence ([Section 6.1.6.1](#)) or for other reasons as deemed necessary by the study investigator.

The following procedures are to occur during the TC/RN visits:

Site TC visits:

- Assess for AEs.
- Assess for suspected pericarditis recurrence events.
- Evaluate concomitant medications as well as pericarditis concomitant medications.
- Additional discussion/assessment as needed.
- Confirm and review upcoming visit arrangements.
- Instruct the subject to bring used and unused study drug vials (those not yet obtained by visiting RN) to the next clinic visit.

RN home visits:

- Obtain central laboratory samples for CRP.
- Provide review of self-administration of the study drug as needed.

- Monitor administration of the study drug (whenever possible).
- Obtain used study drug vials and materials.

The following procedures are to occur during the clinic visits (except for Week 24; see below):

- Assess for AEs.
- Assess for suspected pericarditis recurrence events.
- Evaluate concomitant medications as well as pericarditis concomitant medications.
- Record height and body weight.
- Obtain central laboratory samples for chemistry, hematology, and CRP.
- Obtain central laboratory sample for PK and biomarkers (Weeks 8 and 24 only).
- Obtain central laboratory sample for ADAs (Week 24 only).
- Have all subjects complete the PGIPS score.
- The investigator is to complete the PGA-PA.
- Additional discussion/assessment as needed (i.e., remind the subject about daily pericarditis pain NRS entry).
- Obtain used and unused study drug vials for study drug compliance evaluation.

Upon completion of the above study activities, study drug dispensing can commence. The following procedures occur:

- Obtain weight for pediatric drug dispensing and dosing ([Table 5–1](#)).
- Monitor administration of the study drug dose (whenever possible) and have the subject record in the medication diary.
- Dispense study drug through the IWRS and record the amount (number of vials) dispensed.

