6.1.3.1 RW WEEK 24: Clinic Visit

The Week 24 visit in the clinic includes the following assessments and procedures:

- Assess for AEs.
- Assess for suspected pericarditis recurrences.

- Evaluate concomitant medications as well as pericarditis concomitant medications.
- Perform a full physical examination, height and body weight.
- Acquire a 12-lead ECG.
- Acquire a cardiac ECHO for core laboratory central review; the ECHO is to be read locally before sending to the core lab.
- Obtain an MRI (for substudy participants only).
- For subjects ≥ 18 years, complete the SF-36, EQ-5D-5L, ISI.
- For all subjects, complete the PGIPS score.
- The investigator is to complete the PGA-PA.
- Obtain central laboratory samples for chemistry, hematology, lipid panel, CRP, PK, ADAs, and biomarkers.
- Obtain used and unused study drug vials for study drug compliance evaluation.
- Additional discussion/assessment as needed (i.e., remind the subject about daily pericarditis pain NRS input).

Upon completion of the above study activities, the study drug dispensing can commence. The following procedures occur:

- Obtain weight for pediatric drug dispensing and dosing ([Table 5-1](#)).
- Have the subject administer the RW Week 24 study drug dose (if within the study drug window) and have the subject record it in the medication diary.
- Dispense study drug through the IWRS and record the amount (number of vials) dispensed.
- Review the study drug dosing schedule, administration techniques, and documentation.
- Confirm upcoming study visits.

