6.1.6.2 End of Treatment Visit: Clinic

The EOT visit is to be conducted when a subject permanently discontinues study drug. For subjects who complete the RW period but do not consent to participate in the LTE period, the EORW and EOT visit can be combined. For those subjects who do consent to participate in the LTE period, the EOT visit can be combined with the LTE Week 24 visit. In the event that a subject prematurely discontinues study drug, it is expected that the subject will have an EOT visit as soon as possible and continue to be followed as described in [Section 4.2.2](#).

The EOT visit procedures are as follows:

- Evaluate concomitant medications as well as pericarditis concomitant medications.
- Acquire a 12 lead ECG.
- Acquire a cardiac ECHO for core laboratory central review; the ECHO is to be read locally prior to submission to the core lab.
- Perform a cardiac MRI (for sub-study participants only) only if the previous MRI was done longer than 6 months ago.
- Perform a full physical examination.
- For subjects >18 years, complete the SF-36, EQ-5D-5L, ISI.
- For all subjects, complete the PGIPS score.
- The investigator is to complete the PGA PA.
- Obtain central laboratory samples for chemistry, hematology, lipid panel, CRP, PK, ADAs, biomarkers, and urinalysis.
- Assess for AEs.
- Assess for pericarditis recurrence events.
- Arrange SFU visit.

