6.3.1 Physical Examination

A full physical examination should include at minimum an evaluation of vital signs, head, eyes, ears, nose, and throat as well as cardiovascular, dermatological, musculoskeletal, respiratory, GI, genitourinary, and neurological systems. Body weight and height will be measured as per the [Study Schedule of Activities](#) and will be recorded in the eCRF. Any abnormality identified at baseline should be recorded on the medical history and physical examination eCRFs. At selected visits as specified in the Study Schedule of Activities, an abbreviated physical examination will be performed to evaluate vital signs, lung and heart sounds, including evaluation for pericardial rub.

At all visits at the study site, limited symptom-directed physical examinations may need to be performed in order to determine changes from baseline or abnormalities and should be recorded in the subject's trial notes. New or worsened abnormalities should be recorded as AEs on the Adverse Event eCRF.

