6.3.2 Vital Signs

Vital signs include measurements of respiratory rate, pulse rate, systolic and diastolic blood pressure, and temperature. Blood pressure measurements should be obtained after the subject has been seated for at least 5 minutes.

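### Children dosed in the long-term extension have no scheduled height after LTE baseline, so as much as 24 further weeks on open-label rilonacept go without one

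*Protocol*

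**What the plan says.** Up to the start of the extension, height is measured regularly. Table 1-1 marks body weight and height at RI baseline and RI Week 12. Table 1-2 marks them at RW Weeks 8, 16 and 24, at later RW clinic visits, and at EORW. The RW text agrees: ordinary clinic visits are to "Record height and body weight" (Section 6.1.3), and RW Week 24 is to "Perform a full physical examination, height and body weight" (Section 6.1.3.1). EORW has the same combined entry (Section 6.1.3.2). EORW falls on the same day as LTE baseline, so a height is available when LTE dosing starts.

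After LTE baseline the entries change:

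- Table 1-3 has no row for body weight and height. Its only body measurement is pediatric weight for dosing at LTE Weeks 8 and 16, matched in Section 6.1.4.1 by "Obtain weight for pediatric drug dispensing and dosing".
- LTE Week 24 (Section 6.1.4.2) lists "Perform a full physical examination" with no height or weight. The EOT visit (Section 6.1.6.2) does the same.
- LTE Weeks 30 and 48 list no height.
- Table 1-4 marks height for the unscheduled recurrence visit only, and leaves EOT and safety follow-up blank.

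Protocol versions 1.0 and 1.1 agree on all of this.

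**The concern.** The trial admits subjects from age 12, and Section 3.1.4 offers them open-label drug in the LTE-TP. The prescribing information appended as Section 13.1 (label section 8.4) says that an effect on bone development in children is unknown, and recommends appropriate monitoring of growth and development. A last height taken just before the LTE-TP begins means that growth over that period cannot be calculated from scheduled data.

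What is at stake is the safety follow-up of the individual child. The change at LTE Week 24 also looks unplanned: the two comparable visits before it, RW Week 24 and EORW, pair the examination with height, and this one does not.

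**Working it through.** The plan gives no figure to reproduce, so the check compares visit lists and adds simple arithmetic.

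**Does the full physical examination already include height?** Four places bear on this.

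- Table 1-3, footnote c: "Full physical examination includes at minimum evaluation of vital signs, head, eye, ear, nose, and throat", followed by other body systems. Height is not listed.
- Section 6.3.2: "Vital signs include measurements of respiratory rate, pulse rate, systolic and diastolic blood pressure, and temperature". Height is not a vital sign.
- Section 6.3.1: "Body weight and height will be measured as per the" schedule of activities. Height is set by the schedule and not by the content of the examination.
- Section 6.1.3.1: "Perform a full physical examination, height and body weight". Height is named in addition to the examination.

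So at LTE Week 24 and EOT the examination entry alone does not schedule a height. A site may still take one, because the examination content is a minimum.

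**Scheduled heights before and after LTE baseline, with the shortest RW period.**

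- Before LTE dosing: RI baseline, RI Week 12 and RW Weeks 8, 16 and 24 make 5. EORW makes 6, or the total stays at 5 if EORW coincides with RW Week 24. These cover 12 + 24 = 36 weeks.
- After LTE baseline: 0 at the five later visits (Weeks 8, 16, 24, 30 and 48), and 0 at a stand-alone EOT.
- Longest treated interval after the last scheduled height: 24 weeks × 7 = 168 days, visit windows aside.

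**Share of rilonacept exposure after the last scheduled height, for a child who completes the LTE-TP.**

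- Continuous rilonacept, shortest RW: 24 / (12 + 24 + 24) = 24/60 = 40%.
- Continuous rilonacept, 3 years of dosing (the upper projection in Section 3.1.5): 24 / (3 × 52) = 24/156 = 15.4%.
- Randomized to placebo and never given bailout drug (still offered the LTE under Section 4.2.1): 24 / (12 + 24) = 24/36 = 67% of active exposure.

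**Number of children.** Section 4.1 caps pediatric enrollment at 20%: 0.20 × 56 = 11.2, so 11; and 0.20 × 75 = 15. Both are ceilings. No minimum is set, run-in non-responders stop drug, and the LTE is optional.

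**After the fix.** One height at the visit that ends LTE treatment reduces the interval from as much as 24 weeks to 0. It adds 1 × 11 = 11 to 1 × 15 = 15 readings at most.

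**The case against.** The strongest reply is that nothing here is wrong. Tables and text agree with each other, growth is neither an objective nor an endpoint, and the label sets no measure, interval or end-of-treatment height. Five or six heights are taken before LTE dosing, pediatric weight continues at LTE Weeks 8 and 16, and the examination at LTE Week 24 and EOT includes the musculoskeletal system. A new clinically significant examination finding must be reported as an adverse event (Section 6.4.3.2), and a recurrence visit includes height. Most of this stands, and it limits the point to a small improvement. It does not remove the gap: none of these provisions schedules a height, and the recurrence visit happens only if there is a suspected event.

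A reader might infer three stronger things that the documents do not support.

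- That the LTE has no height at all. EORW is the LTE baseline visit and includes height, so the gap begins after that visit.
- That every EOT visit leaves a child unmeasured. A randomized child who stops drug in the RW period still has EORW with height, and a child who does not enter the LTE may combine EOT with EORW. Only children dosed in the LTE-TP are affected.
- That the protocol contradicts the label. The label asks for appropriate monitoring and leaves the form open, so the schedule can fall short of good practice without conflicting with it.

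**Conclusion.** The point holds as a minor gap in pediatric safety monitoring, limited to children who receive drug in the LTE-TP. For them no height is scheduled after LTE baseline, and as much as 24 weeks of treatment follow.

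The 40% share is a ceiling for continuous rilonacept; it assumes the shortest RW period and a full LTE-TP. The counts of 11 and 15 assume that the pediatric cap is filled and that every enrolled child goes on to LTE dosing, so the true number may be much lower or zero. Pediatric dosing uses weight and is unaffected, as are the endpoints, alpha and power. Severity is low. The change is worth making because it costs so little and the label leaves bone development in children as an open question.

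**What to change.** For subjects under 18 at entry, add one height at the visit that ends LTE treatment: LTE Week 24, or EOT if drug is stopped earlier in the LTE-TP. Add a pediatric height row to Table 1-3 marked at LTE Week 24, mark height at EOT in Table 1-4 with a footnote limiting it to children who stop during the LTE-TP, and add matching lines to Sections 6.1.4.2 and 6.1.6.2. Placing it at LTE Week 24 alone would miss a child who stops early.

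Because "the EOT visit can be combined with the LTE Week 24 visit" (Section 6.1.6.2), no child needs two readings. Body weight need not be added to close this gap, and heights at LTE Weeks 8 and 16 are optional. The cost is a minor schedule amendment covering two tables and two sections, which can go with the next amendment, and at most 11 to 15 extra height readings at clinic visits already planned.

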6.1.5 LTE Follow-Up Period

Upon completion of the LTE Week 24 EOT visit, subjects continue long term follow-up until the end of the study (EOS). The LTE-FUP includes 2 visits.

6.1.5.1 LTE Week 30 Visit: Clinic

The LTE Week 30 visit is a clinic visit. Visit activities are as follows:

- Assess for AEs.
- Evaluate concomitant medications as well as pericarditis concomitant medications.
- Assess for pericarditis recurrence events.
- Additional discussion/assessment as needed.
- Obtain central laboratory samples for CRP, ADAs, and urine pregnancy test.
- Any left-over ancillary supplies are to be returned to the site.

6.1.5.2 LTE Week 48 End of Study Visit: TC

The LTE Week 48 EOS TC visit procedures are as follows:

- Assess for AEs.
- Evaluate concomitant medications as well as pericarditis concomitant medications.
- Assess pericarditis recurrence.

6.1.6 Supplemental Visits

6.1.6.1 Pericarditis Recurrence Assessment: Clinic Visit

If a subject experiences symptoms consistent with pericarditis recurrence, he/she should contact the study investigator immediately for evaluation. It is possible that a subject may have assessments performed remotely, however, assessments are also expected to be performed at the study site as soon as possible. Required assessments include:

- Evaluate pericarditis pain on the 11-point NRS.
- Evaluate concomitant medications as well as pericarditis concomitant medications.
- Obtain laboratory samples for CRP (local and central) (the POC device provided by Kiniksa Pharmaceuticals is the preferred method for local laboratory CRP assessment).
- Acquire a 12 lead ECG.
- Acquire a cardiac ECHO per core laboratory imaging parameters; this ECHO is read locally for the purpose of pericarditis recurrence assessment and is then submitted to the ECHO core laboratory for central review.
- Perform an abbreviated physical examination, height and body weight.
- For subjects >18 years, complete the SF 36, EQ-5D 5L, ISI.
- For all subjects, complete the PGIPS score.
- The investigator is to complete the PGA PA.
- Obtain central laboratory samples for PK, ADAs, and biomarkers.
- Other procedures deemed necessary per the investigator or delegated site personnel.

Upon having completed the evaluation, if the investigator makes a clinical diagnosis that the subject is having a pericarditis recurrence event, he/she should contact the [REDACTED] medical monitor to review and confirm that all assessments have been performed and collected. Upon [REDACTED] medical monitor confirmation of completion of the assessment, the investigator commences as described in [Section 6.2.3](#).

Subjects treated for a pericarditis recurrence event will continue to follow the same visit schedule described for the RW period ([Section 6.1.3](#)).

Source documentation including the assessments and evaluations used to confirm a pericarditis recurrence event, are required to be sent to CEC.

6.1.6.2 End of Treatment Visit: Clinic

The EOT visit is to be conducted when a subject permanently discontinues study drug. For subjects who complete the RW period but do not consent to participate in the LTE period, the EORW and EOT visit can be combined. For those subjects who do consent to participate in the LTE period, the EOT visit can be combined with the LTE Week 24 visit. In the event that a subject prematurely discontinues study drug, it is expected that the subject will have an EOT visit as soon as possible and continue to be followed as described in [Section 4.2.2](#).

The EOT visit procedures are as follows:

- Evaluate concomitant medications as well as pericarditis concomitant medications.
- Acquire a 12 lead ECG.
- Acquire a cardiac ECHO for core laboratory central review; the ECHO is to be read locally prior to submission to the core lab.
- Perform a cardiac MRI (for sub-study participants only) only if the previous MRI was done longer than 6 months ago.
- Perform a full physical examination.
- For subjects >18 years, complete the SF-36, EQ-5D-5L, ISI.
- For all subjects, complete the PGIPS score.
- The investigator is to complete the PGA PA.
- Obtain central laboratory samples for chemistry, hematology, lipid panel, CRP, PK, ADAs, biomarkers, and urinalysis.
- Assess for AEs.
- Assess for pericarditis recurrence events.
- Arrange SFU visit.

